7.3. Baseline visits

One hundred and fifty healthy subjects who fulfil the eligibility criteria will be recruited to the study. Baseline visits will be scheduled at day 0 and day 7 (visit 2 and 3). Baseline visits will include capillary blood and venous blood collection (Appendix C). Randomization will be performed during visit 2.

For baseline and subsequent visits, in case participant fails to come on the exact day a visit is scheduled, he/she will be allowed to come for a retake any other working day of the study team until the next scheduled visit.

7.4. Randomization

A block randomization schedule will be generated using the block.random() function of the R package *psych* version 1.8.12 using variables species (*An. minimus, An. maculatus, An. dirus, Ae. aegypti* and *Ae. albopictus*) and dose (35 or 305 bites in total) yielding a list of 15 blocks with 10 participants each (total of 150 participants). Following screening and eligibility assessment, participant will be assigned a study arm during visit 2 through the randomization schedule. Individual, sealed and sequentially numbered envelopes will be provided for the study site with one envelope per participant, indicating the allocation.

7.5. Subsequent visits

From day 14 to day 56, participant will be exposed to bites of laboratory-adapted colonies of Anopheles minimus, An. maculatus and An. dirus, Aedes aegypti or Ae. albopictus reared at the SMRU. Appropriate quality control measures will be implemented such as to guarantee the absence of human pathogen in the mosquito batches used in this study and withdraw any participant with hypersensitivity to mosquito bites (see section 13.5.1. Risk of mosquito exposure). Participants will receive a total of either 35 or 305 mosquito bites per participant in 7 challenges split over 6 weeks (see mosquito intervention section). Each visit will include physical examination, vital signs assessment, mosquito exposure, capillary blood and venous blood collection according to Appendix C. Immediate skin reactions (20-30 min after mosquito bites) will be recorded after each mosquito feeding assay. Delayed skin reactions (24-36 hours after mosquito bites) will be recorded after the day 14, 21 challenges, requiring additional visits at day 15, 22. After day 56, each visit will include capillary blood and venous blood collection according to Appendix C. The study procedure will take approximatively 1 hours for medical history assessment, physical examination and vital sign assessment, 15 minutes for blood sampling and 30-90 minutes for the challenge with mosquito bites (depending on the number of repeats needed to reach the target number of mosquito bites). During the exposure visits, the participants will be kept in observation for an additional hour after the challenge before being allowed to leave the study site. Participants will be requested not to apply any lotions, ointments, creams, powders, perfumes, antiperspirants, repellents, or attractants prior to each exposure visit. Participants will be provided palliative antipruritic medication consisting in 1% diphenhydramine hydrochloride cream and oral cetirizine at the dose of 10 mg per day in order to relieve itching from mosquito bites (103, 104). In addition, participants will be provided with a mosquito bed net and skin repellent in order to minimize uncontrolled natural exposure to mosquito bites that can happen independently of the study challenges.

7.6. Blood collection

Both capillary blood and venous blood will be collected weekly from each study participant over 112 days with an additional venous sample collected during the screening visit, yielding 17 capillary blood samples (5.1 mL of capillary blood in total) and 18 venous blood samples (178.2 mL of venous blood in total) per study participant (Appendix C). Venous blood samples will be collected by venepuncture. In addition, participants will undergo a finger-prick using a single usage sterile lancet, from which capillary blood will be collected on filter paper in order to constitute three DBS. All blood samples will be collected on site by SMRU study teams (trained and qualifies medics, nurses and medical doctors). The volume of blood collected in this study is justified based on the technical requirement to perform the assays in the different collaborative centres (see details below) (53, 101).

7.7. Specimen/sample handling

Sample pre-treatment, storage and shipment:

Venous blood samples will be spun down to separate the serum. Three serum aliquots of 2 mL, 2 mL and 0.1 mL each will be made during visits 2, 3, 4, 6, 8, 9, 10, 11, 12, 13, 14, 15, 16, 17, 18, 19 and 20. Moreover, an additional 5 mL serum aliquot be made during visits 4, 13 and 20. Hence, 8.6 mL of venous blood will be collected from participants during visits 2, 3, 6, 8, 9, 10, 11, 12, 14, 15, 16, 17, 18 and 19 (4.1 mL of serum in total), and 18.6 mL of venous blood will be collected during visits 4, 13, 20 (9.1 mL of serum in total). The volume of blood was calculated considering a 50% hematocrit (upper limit of the reference range) and an additional 0.2 mL of buffer volume of serum (0.4 mL of blood) to avoid contamination with

the buffy coat when preparing the serum aliquots. Spotted capillary blood will be dried at room temperature. Dry blood spot specimens will be put into a zip lock bag containing silica gel. DBS and serum aliquots will be stored at -20°C until shipment to the collaborative centres. Coded specimen will be shipped to the Burnet Institute (Melbourne, Australia) for ELISA and immuno-proteomic analysis, the Singapore Immunology Network (Agency for Science, Technology, and Research, Singapore) for ELISA and to the Walter Reed Army Institute of Research (Silver Spring, United States of America) for mesoscale screening. No personally identifiable information will be transferred. Samples will be kept accessible only by authorised researchers.

A 2-mL serum aliquot and the DBS samples collected during visits 2, 3, 4, 6, 8, 9, 10, 11, 12, 13, 14, 15, 16, 17, 18, 19 and 20 will be shipped to the Burnet Institute (Melbourne, Australia) for doing ELISA screening. A 2-mL serum aliquot collected during visits 2, 3, 4, 6, 8, 9, 10, 11, 12, 13, 14, 15, 16, 17, 18, 19 and 20 will be shipped to the Singapore Immunology Network (Agency for Science, Technology, and Research, Singapore) for doing ELISA screening. A 0.1-mL serum aliquot collected during visits 2, 3, 4, 6, 8, 9, 10, 11, 12, 13, 14, 15, 16, 17, 18, 19 and 20 will be shipped to the Walter Reed Army Institute of Research (Silver Spring, United States of America) for doing mesoscale screening. The 5-mL serum aliquots collected during visits 4, 13 and 20 will be shipped to the Burnet Institute (Melbourne, Australia) for being analysed with immuno-proteomic methods.

Enzyme-linked immunosorbent assay procedures:

Antibody titer against a broad panel of candidate peptides will be determined on the serum specimens. This panel will include, but will not be limited to, five peptides specific to each mosquito species, in addition to the *Anopheles gambiae salivary* peptide SG6-P1 (target of 10 peptides per panel). Serial dilution of the serum specimens will be carried out in order to determine antibody titer (the titer is defined as the last dilution giving a positive response; a positive response is defined as the mean + 3 standard deviation of naive serum used as negative control) (101). Each sample will be tested in duplicate with a reaction volume of 100 uL. Therefore, the volume of serum needed for each peptide is 200 uL of serum /peptide (2 mL of serum for 10 peptides). Dry blood spots will be eluted separately in 200 uL of PBS such as to have 3 technical replicates and analysed using the same ELISA protocol. Samples will also undergo further serological analyses for antigen and antibody characterisation, including but not limited to competition ELISAs (to quantify the antibody/antigen interaction) (100), functional antibody assays (*e.g.* complement fixation assays) (101).

Mesoscale assay procedures:

The serum specimens collected will be diluted 250 folds and applied to test plates. The testing will require 750 uL diluted sample (3 uL of neat serum) per test panel. A minimum volume of 6 uL of neat serum is needed in case technical issue happens and rerun is needed. It is impossible to ship such small volumes (evaporation/drying up) and therefore a minimum of 100 uL will be sent.

Immuno-proteomic procedure:

Immuno-proteomic analysis will be carried out using a procedure adapted from previously published studies (53, 102, 107). This analysis will be performed with the 5 mL serum aliquots collected from study participants during visit 4 (baseline), visit 13 (early after exposure period) and visit 20 (end of the post-exposure period). Single serum specimens will be used in order to assess inter-individual variation of the antibody response against salivary gland proteome.

Two-dimensional gel electrophoresis will be performed with protein extracts made from the dissected salivary glands of 200 female adult mosquito specimens. In order to obtain a sufficient resolution, protein separation will be done on an 11 cm × 20 cm gel format. The gel proteins will be then transferred to a membrane. The membrane will be incubated with 50 mL of serum diluted 10 folds (5mL of neat serum) in order to assess the reactivity of serum IgG by Western blot (53). Reactive spots of interest will be detected by comparing the staining patterns from baseline, end of exposure and post-exposure samples. Spots of interest will be excised from the 2D gel and used to perform in gel digestion with trypsin. The protein digest will be analysed with liquid chromatography-mass spectrometry. Immunogenic proteins will be identified by searching the mass spectra with Mascot (Matrix Science Ltd.).

7.8. Storage of Specimens/samples

Left over specimens will be stored no longer than 10 years using codes assigned by the investigators or their designee(s). Access to research samples will be limited using either a locked room or a locked freezer. Only investigators or their designee(s) will have access to the samples.

In the future, investigators from this protocol and other investigators besides those listed in this protocol may wish to study these samples. A proposal of the planned research will be submitted to the IRB for their consideration.

7.9. Discontinuation/Withdrawal of Participants from Study

Each participant has the right to withdraw from the study at any time.

In addition, the Investigator may discontinue a participant from the study at any time if the Investigator considers it necessary for any reason including:

- Ineligibility (either arising during the study or retrospectively having been overlooked at screening)
- Significant protocol deviation
- Significant non-compliance with study requirements
- Loss to follow up
- Hypersensitivity to mosquito bites or anaphylaxis

The data collected until the point of withdrawal will be included in the study and this is stated in the participant information sheet unless participant refuse to do so. The participant will be replaced with another person and the replacement will be assigned to the same study arm.

7.9. Definition of End of Study

The end of the study is defined as the last day of sample collection from the last participant.

8. MOSQUITO INTERVENTION

From day 14 to day 56, participant will be exposed to bites of laboratory-adapted colonies of *An. minimus, An. maculatus* and *An. dirus, Ae. aegypti* or *Ae. albopictus* reared at the SMRU. Appropriate quality control measures will be implemented such as to guarantee the absence of human pathogen in the mosquito batches used in this study and withdraw any participant with hypersensitivity to mosquito bites (see section 13.5.1. Risk of mosquito exposure). In the low-exposure groups, participants will be exposed to 5 mosquito bites at weekly intervals from day 14 to day 56 (seven challenges with 5 mosquito bites/challenge over six weeks, yielding a total of 35 mosquito bites). In the high-exposure group,

participants will be exposed to 5 mosquito bites on day 14 and then to 50 mosquito bites at weekly intervals from day 21 to day 56 (one challenge with 5 mosquito bites and six challenges with 50 mosquito bites/challenge over 6 weeks, yielding a total of 305 mosquito bites).

For the low-dose challenge, five 5 to 7-day-old nulliparous female imagoes (i.e. that have never blood fed before) will be introduced individual into 50 mL plastic tube covered with netting material. For high-dose challenge, 47 mosquitoes will be split into four plastic cups of 10 cm in diameter covered with netting material (three cups with 12 mosquitoes and one cup with 11 mosquitoes), and 3 mosquitoes will be introduced individually into 50 mL plastic tubes. At first, three mosquito bites from individual 50 mL tubes will be administered on participant's arm. Then, the remaining mosquito containers will be placed on participant's left arm, calf, thigh or back skin, and the lights will be dimmed to encourage mosquito bites administered on participant's arm will be used to assess immediate and delayed skin reactions as described previously (37). Immediate and delayed skin reactions will be recorded respectively 20-30 min and 24-36 hours after the day 14 and day 21 challenges, requiring additional visits at day 15 and 22.

Mosquitoes will be given the opportunity to feed on participant's skin for 30 min. The number of bites actually received by participants will be assessed by counting the number of engorged mosquitoes at the end of the 30-minute exposure time. If not all mosquitoes would have successfully engorged, participant will be exposed to additional mosquitoes using the same procedure in order to reach the target number of bites (participant may be exposed to mosquito bites up to three times at each visit). Partially engorged mosquitoes will not be discarded and we be counted as fully engorged specimens. In case the challenge will be carried out in the morning, mosquitoes will be starved overnight. In case the challenge will be carried out in the afternoon, mosquitoes will be staved since 9 am. Mosquitoes used to challenge each study participant will be immediately killed at the end of the challenge using 70% ethanol. The mosquito exposure will be performed by study staff under supervision of a medical doctor. The challenge with mosquito bites will take 30 minutes and may be repeated twice in case not all mosquito engorge during the first challenge. The participants will be kept in observation for an additional hour before being allowed to leave the study site. During that time, participants will be provided with a snack and refreshment.

9. SAFETY REPORTING

9.1. Definition of Serious Adverse Events

A serious adverse event (SAE) is any untoward medical occurrence that:

- results in death;
- is life-threatening;
- requires inpatient hospitalisation or prolongation of existing hospitalisation;
- results in persistent or significant disability/incapacity.

The term "life-threatening" in the definition of "serious" refers to an event in which the participant was at risk of death at the time of the event; it does not refer to an event which hypothetically might have caused death if it were more severe.

9.2. Reporting Procedures for Serious Adverse Events

A SAE occurring to a participant should be reported to ethic committee at the Faculty of Tropical Medicine, Mahidol University and to the Safety Review Board within 5 working days of investigator's awareness.

9.3. Adverse event (AE)

At each visit, a CRF and an AE form will be completed. AEs will be documented according to standard definitions and procedures following the Common Terminology Criteria for Adverse Events version 5.0 guidelines (108). Pre-specified AEs include blood and lymphatic system disorders (leucocytosis and eosinophilia), general disorders and administration site conditions (chills, fatigue, fever, challenge site reaction, malaise, pain, challenge site lymphadenopathy), immune system disorders (allergic reaction, anaphylaxis), infections and infestations (papulopustular rash, rash pustular, sepsis, skin infection), injury, poisoning and procedural complications (bruising, venous injury), skin and subcutaneous tissue disorders (bullous dermatitis, eczema, erythema multiforme, pain of skin, pruritus, rash acneiform, rash maculo-papular, skin induration, skin ulceration, urticaria, skin atrophy, skin hyperpigmentation, skin hypopigmentation). Definition and detailed grading procedure of pre-specified adverse events are given in the Appendix E. Any unexpected AEs will be recorded according to the same guidelines.

9.4. Safety review board

All data from the study participant will be submitted to a safety review board after days 15 and 22 in order to review the adverse events (AEs) and decide whether the participant should be withdrawn from the study. Reactions that will exclude the participant include immediate or delayed local reactions greater than 30 mm diameter, any ecchymotic, vesicular, blistering or bullous manifestation, Skeeter syndrome or any systemic symptom (e.g. generalized urticaria, angioedema or anaphylaxis).

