each of the study condition (Appendix B). Participants will be in the study for 112 days (Appendix C). The baseline will consist of 2 visits over 2 weeks (day 0 and day 7). In the low-exposure groups, participants will be exposed to 5 mosquito bites at weekly intervals from day 14 to day 56 (seven challenges with 5 mosquito bites/challenge over six weeks, yielding a total of 35 mosquito bites). In the high-exposure group, participants will be exposed to 5 mosquito bites on day 14 and then to 50 mosquito bites at weekly intervals from day 21 to day 56 (one challenge with 5 mosquito bites and six challenges with 50 mosquito bites/challenge over 6 weeks, yielding a total of 305 mosquito bites). The number of bites and modalities of the follow up used in this study were chosen based on previous entomological investigation conducted in this area (10, 11, 96), published reports of human challenge with mosquito bites (37, 97-99) and current knowledge on the characteristic of the humoral response against saliva antigens (31, 37, 52). Both immediate and delayed skin reactions will be recorded after day 14 and day 21 challenges, requiring additional visits at day 15 and day 22. Participants with hypersensitivity to mosquito bites will be withdrawn from the study. Both capillary and venous blood samples will be collected weekly from each study participant (Appendix D). Eighteen venous blood samples will be collected including one sample of 2 mL drawn during screening visit, 14 samples of 8.6 mL during visits 2, 3, 6, 8, 9, 10, 11, 12, 14, 15, 16, 17, 18 and 19, and 3 samples of 18.6 mL during visits 4, 13 and 20 (178.2 mL of venous blood per participant in total). Seventeen dry blood spot (DBS) samples will be made from of 300 uL of capillary blood collected during visits 2, 3, 4, 6, 8, 9, 10, 11, 12, 13, 14, 15, 16, 17, 18, 19 and 20 (5.1 mL of capillary blood per participant in total). Candidate peptides will be identified in silico using publicly available genomes sequences and B-cell epitope prediction algorithms. The kinetic of antibody titers against candidate biomarkers will be assessed by enzyme-linked immunosorbent assay (ELISA) and mesoscale screening performed with serum and DBS specimens (100). Briefly, the positivity threshold of the assay will be determined using reference sera specimens from individuals not exposed to mosquito bites, as described previously (62). The ELISA signal measured in 60 reference sera obtained from unexposed individuals (30 Thai sera obtained from the Thai Red Cross and 30 Australian sera obtained from the Burnett Intstitute) will be used to define the positivity threshold of the assay. The positivity threshold of the assay will be defined as three standard deviation (SD) above the mean optic density (Δ OD) measured for the unexposed control population. A test in the study population with a ΔOD above this cut-off will be considered positive (i.e. an immune response). The specific antibody titer of study samples will be determined by performing serial dilution experiments (101). Serial dilution will be made from study samples and the Δ OD will be determined for each dilution. The antibody titer will be defined as the highest dilution giving a positive signal. Results obtained with DBS and serum specimens will be compared in order to assess the feasibility of using DBS samples to monitor exposure to bites of mosquitoes during epidemiological studies. Serum specimens collected during visits 4 (baseline), 13 (early after the end of exposure) and 20 (post-exposure) will also be analysed with immuno-proteomic approach (2D gel electrophoresis of salivary gland protein extracts, Western blot and mass spectrometry) yielding additional information on the antigenic properties of mosquito salivary gland proteome (102).

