A few previous studies reported the safety of human challenges performed with large numbers of (infected) malaria mosquito bites and no serious adverse event was observed (97-99). Immediate skin reactions (20-30 min after mosquito bites) will be recorded after each mosquito feeding assay. Delayed skin reactions (24-36 hours after mosquito bites) will be recorded after the day 14, 21, requiring additional visits at day 15, 22. All data from study participant will be submitted to a safety review board after day 15, 22 for reviewing potential adverse events (AEs) and eventually request withdrawal of the participants from the study. Reactions that will exclude the participant include immediate or delayed local reactions greater than 30 mm diameter, any ecchymotic, vesicular, blistering or bullous manifestation, Skeeter syndrome or any systemic symptom (e.g. generalized urticaria, angioedema or anaphylaxis). In addition, all mosquito feeding experiments will be conducted under the supervision of a medical doctor and resuscitation material will be available at the site of the study. In case SAE happen and cannot be managed on site, the participants will be referred to Mae Sot general hospital (located at 5 min from the study site).

Skin infection at the challenge site:

Secondary development of a skin infection may develop at the site of the challenge, especially if severe allergic skin reactions develop (36). Participants with severe reaction to mosquito bites will not be enrolled or will be withdrawn from the study, therefore limiting the risk of skin infection. In addition, the skin will be disinfected with 70% alcohol before the challenge, and appropriate diagnosis and treatment of eventual infection will be ensured during participant follow-up.

Accidental transmission of vector-borne disease causative agents:

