This study is an exploratory, factorial randomized control trial of controlled exposure to mosquito bites with 10 arms corresponding to different species (*An. minimus, An. maculatus, An. dirus, Ae. aegypti* and *Ae. albopictus*) and numbers of bites (35 or 305 bites in total over 6 weeks). Participants will be assigned randomly to one of the 10 study arms with a 1:1 ratio using a block randomization schedule. Those with incomplete follow-up will be replaced until complete follow-up of 15 participants per arm is achieved. Serum from venous blood and capillary blood spotted on filter paper will be collected weekly from each study participant before, during and after the challenges. In addition to those described in the published literature, candidate peptides will be identified with antigen prediction algorithms using mosquito DNA sequences data (either deposited in open access databases (24) or generated using wild-caught mosquito specimens) and immunoproteomic assays carried out using protein extracts of dissected mosquito salivary glands and participants samples (20). Antibody titers will be determined with high-throughput ELISA (25) and mesoscale screening assays (26).

The Statistical Analysis Plan (SAP) for the analysis of "Characterizing antibody responses to mosquito salivary antigens of the Southeast Asian vectors of malaria and dengue with a human challenge model of controlled exposure" (ClinicalTrials.gov Identifier: NCT04478370) describes and expands upon the statistical information presented in the protocol.

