5.2 Study Visit Schedule

Study variables are collected according to the study visit schedule in Table 2.

Visit	Study period	Day ^a	Informed consent obtained	Medical History	PE and VS	Randomization	Mosquito exposure	DBS Collection	VP collection
1	screening	30 days or less before enrolment	Yes	Yes	Yes	No	No	No	Yes
2	baseline	0	No	No	No	Yes	No	Yes	Yes
3	baseline	7	No	No	No	No	No	Yes	Yes
4		14	No	No	Yes	No	Yes	Yes ^c	Yes ^c
5		15	No	No	Yes	No	No	No	No
6		21	No	No	Yes	No	Yes	Yes	Yes
7		22	No	No	Yes	No	No	No	No
8	exposure	28	No	No	Yes	No	Yes	Yes	Yes
9		35	No	No	Yes	No	Yes	Yes	Yes
10		42	No	No	Yes	No	Yes	Yes	Yes
11		49	No	No	Yes	No	Yes	Yes	Yes
12		56	No No Yes No		No	Yes	Yes	Yes	
13		63	No	No	No	No	No	Yes	Yes
14		70	No	No	No	No	No	Yes	Yes
15		77	No	No	No	No	No	Yes	Yes
16	post-	84	No	No	No	No	No	Yes	Yes
17	exposure	91	No	No	No	No	No	Yes	Yes
18		98	No	No	No	No	No	Yes	Yes
19		105	No	No	No	No	No	Yes	Yes
20		112	No	No	No	No	No	Yes	Yes

Table 2 Study Visit Schedule

^d 2 mL during the screening visit, 8.6 mL during visits 2, 3, 6, 8, 9, 10, 11, 12, 14, 15, 16, 17, 18 and 19 and 18.6 mL during visits 4, ^a In case participant fail to come on the exact day a visit is scheduled, he/she will be allowed to come for a retake any other working day of the study team until the next scheduled visit;

^b 5 bites for the screening of hypersensitivity to mosquito bites during visit 4, then 5 or 50 bites/visit according to the randomisation schedule (total of 35 and 305 bites/participant in low- and high-exposure groups respectively, split into 7 direct feeding assays);

^c before exposure to mosquito bites.

13 and 20.

6 Sample Size

There is no data to calculate the sample size *a priori* because the characteristics of immune responses to candidate peptides is not known at this stage. A sample size of 15 participants with complete follow-up per study arm was deemed appropriate for this study given the number of repeated assessments and expected variation in the continuous individual antibody responses. Participants with incomplete follow-up will be replaced to ensure there are 15 participants per study arm with complete follow-up.

7 General Considerations

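### A serious adverse event may be reported to the Safety Review Board as late as, or after, the next weekly challenge, and no hold on the arm is written (minor)

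*Protocol*

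**What the plan says.** **Reporting limit.** Protocol 9.2 requires an SAE to be reported to the ethics committee and "to the Safety Review Board within 5 working days of investigator's awareness". One limit covers every SAE. Nothing faster is given for fatal, life-threatening or challenge-related events.

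**Challenge schedule.** Protocol 5 and 8 set seven weekly challenges from day 14 to day 56. The high-exposure groups receive "5 mosquito bites on day 14 and then to 50 mosquito bites at weekly intervals from day 21 to day 56"; the low-exposure groups receive 5 bites each time. Under Protocol 7.3 a missed visit may be made up on any working day until the next scheduled visit.

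**Board reviews.** Under Protocol 9.4 each participant's data go to the Board after days 15 and 22 "in order to review the adverse events (AEs) and decide whether the participant should be withdrawn from the study". Protocol 13.5.1 repeats this: the data go to the Board "for reviewing potential adverse events (AEs) and eventually request withdrawal of the participants from the study".

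**Withdrawal and replacement.** Protocol 7.9 lets the investigator discontinue a participant at any time, and one listed reason is "Hypersensitivity to mosquito bites or anaphylaxis". It adds: "The participant will be replaced with another person and the replacement will be assigned to the same study arm".

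**The concern.** A challenge study gives healthy volunteers repeated doses of the same exposure. If one volunteer has an SAE that may be due to the challenge, the next question is whether others due for the same colony and dose should proceed. The safety body should be able to consider this before they are exposed again.

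Here the time allowed for telling the Board is as long as the dosing interval, and nothing is written about what happens to the arm in the meantime. At stake is the safety of the other volunteers in that arm, in a study that by Protocol 13.6 offers them no individual benefit. No estimate of an antibody endpoint is affected.

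**Working it through.** **Inputs**
- SAE limit: 5 working days from awareness (Protocol 9.2).
- Challenge days: 14, 21, 28, 35, 42, 49, 56 (Protocol 5 and 8).
- Board reviews: after days 15 and 22 (Protocol 9.4).
- Arms: 10, with 15 participants each (Protocol 7.4; Appendix B).
- Assumption: a Monday-Friday working week without holidays, counting the day of awareness as day 0. The documents do not define a working day.

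**1. The plan's own figures.** Low dose: 7 × 5 = 35 bites. High dose: 5 + 6 × 50 = 305 bites. Participants: 10 × 15 = 150. All agree with the protocol.

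**2. Working days to calendar days.** Five working days from any weekday is 5 + 2 weekend days = 7 calendar days. It is 6 from a Saturday and 5 from a Sunday.

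**3. Against the weekly interval.** Suppose awareness comes on a weekday, k days after a challenge. The limit falls k + 7 days after that challenge. The next challenge for volunteers on the same schedule falls 7 days after it.
- k = 0: the limit and the next challenge fall on the same day.
- k = 2: the limit falls on day 9, two days after the next challenge.

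A public holiday lengthens the limit. A make-up visit shortens the interval to the next challenge.

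**4. Volunteers on other schedules.** SAP 5.1 assigns identification codes in order of enrolment, so volunteers in one arm need not share a challenge day. Between days 14 and 56, any run of 7 consecutive days holds exactly one scheduled challenge per volunteer. A 7-day reporting window therefore covers one challenge for each arm-mate who is mid-schedule. The number affected ranges from 0 (nobody else in the exposure phase) to 14 (all other places in the exposure phase at once). The upper end in a high-dose arm, with everyone past the first challenge, is 14 × 50 = 700 bites. Staggered enrolment would make it smaller.

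**5. Sensitivity to the working week.** On a Monday-Saturday week, 5 working days is 5 or 6 calendar days. The limit for awareness on a challenge day then falls before the next challenge on that schedule, but arm-mates challenged on other weekdays can still come first.

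**6. What the scheduled reviews cover.** After the day-22 review, five challenges remain (days 28 to 56). That is 5 × 50 = 250 of 305 bites (82%) in a high-dose arm and 5 × 5 = 25 of 35 (71%) in a low-dose arm. For an SAE in that period, 9.2 is the only stated route to the Board.

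**7. Search for a hold.** Protocol 7.9, 8, 9.2 to 9.4 and 13.5.1 contain withdrawal rules for the individual. None pauses challenges or replacements in an arm. The SAP has no such rule either.

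**The case against.** **The case on the other side is substantial.**
- The people who can act already know. The limit runs from investigator awareness, the study has one site, a doctor supervises each challenge, participants are observed for an hour, and the investigator may discontinue anyone at once. This stands, and it is the main reason the point is minor. It does not give the Board the question in time.
- Five working days is a maximum. An event around days 14-15 or 21-22 may reach the Board sooner through the scheduled submission. This stands for those two visits, although 9.4 sets no deadline before the next challenge.
- The ethics committee also receives every SAE. That adds outside oversight, but under the same limit.
- Protocol 13.5.1 cites earlier human challenges with large numbers of infected malaria-mosquito bites and no SAE. This lowers the expected frequency. It does not cover the two *Aedes* species.
- Protocol 12 refers to standard operating procedures that are not reproduced, and a hold may be written there. The finding is that the protocol and SAP contain none, not that none exists.

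**Two stronger readings are tempting.** First, a reader might infer that the person with the SAE is left exposed. Protocol 7.9 and 8 provide for that person's withdrawal, so this is not supported.

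Second, a reader might infer that replacing withdrawn reactors without a cap, until as SAP 1.1 says "Those with incomplete follow-up will be replaced until complete follow-up of 15 participants per arm is achieved", needs a reactor count or limit by arm or species. The documents do not support this as a defect. Their only rate for large local reactions is 2.5%, self-reported, with 8 of 12 cases in children under 10 (Protocol 13.5.1). At that rate the expected number exposed per arm is 15/(1 − 0.025) = 15.38, or about 3.8 extra volunteers over ten arms. An assumed 20% would give 15/(1 − 0.20) = 18.75 per arm, but nothing in the documents suggests a rate eight times the cited one in adults screened for hypersensitivity and atopy. Any threshold would be the reviewer's own.

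**Conclusion.** The concern holds as a minor gap in SAE handling. On a Monday-Friday week, the Board may properly be told of a challenge-related SAE on the day of the next weekly challenge or after it, and neither document holds the arm in the meantime. The conclusion about arm-mates on other challenge days also holds on a six-day week.

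Its size is a reporting window of up to 7 calendar days (longer with holidays), which spans one challenge for each arm-mate who is mid-schedule. No expected number of harms can be given, because the documents state no SAE rate and the only experience they cite had none. The conclusion needs no assumption about the reaction rate. It does not extend to a cap on replacement or a reactor tally; those are optional design preferences.

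**What to change.** Add to Protocol 9.2, in substance: *An SAE possibly related to a mosquito challenge is reported to the Board at once, and in any case before the next challenge of any participant in the same species-dose arm. Challenges and replacements in that arm are held until the Board responds.* The 5-working-day limit can stay for unrelated SAEs and for the ethics committee.

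The cost is a short delay in one arm after a rare event, and a Board that can be reached at short notice. No new committee, visit or sample is needed. The make-up rule in Protocol 7.3 can absorb a hold that ends before the next scheduled visit. A longer one could cost a challenge, leaving volunteers short of 35 or 305 bites, or push visits out of window under SAP 8.3.

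Timing matters. SAP 7.1 reads as though the day-112 follow-up was complete when version 1.2 was dated (March 2023), although the protocol synopsis plans the study to December 2023. If follow-up has ended, the change can apply only to later challenges with these colonies.
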